#### **10.4.1** Adverse Events Definitions

For the purposes of this study, adverse events include: all ocular AEs; all ocular and non-ocular serious adverse events (SAEs); adverse device effects (ADEs); and serious adverse device effects (SADEs). Non-ocular adverse events other than non-ocular SAEs will not be collected because of their lack of influence on assessing safety of the Test and Control IOLs. AEs, SAEs, ADEs and SADEs are defined as follows.

An adverse event (AE) is any untoward medical occurrence, unintended disease or injury, or untoward clinical sign (including abnormal laboratory finding) in a subject, user or other persons, whether or not related to the investigational medical device. This definition includes events related to the medical device or procedures involved. For users or other persons, this definition is restricted to events related to the study device.

A Serious Adverse Event (SAE) is an AE that leads to:

- death
- a serious deterioration in the health of the subject that either results in:
  - o a life-threatening illness or injury, or
  - o a permanent impairment of a body structure or body function (e.g., blindness), or
  - o in-patient or prolonged hospitalization, or
  - o a potentially vision-threatening condition, or

- o medical or surgical intervention to prevent life- or vision-threatening illness or injury or permanent impairment to a body structure or a body function
- fetal distress, fetal death, or a congenital abnormality or birth defect

Planned hospitalization for a pre-existing condition will not be considered a serious adverse

An Adverse Device Effects (ADE) is any adverse event related to the use of an investigational medical device or an approved medical device used as a comparator. This definition includes any events resulting from insufficient or inadequate instructions for use, deployment, implantation, installation or operation, or any malfunction of the investigational medical device. This definition also includes any event resulting from device malfunction, use error, inadequate labeling, or from intentional misuse of the investigational medical device.

A Serious Adverse Device Effect (SADE) is any ADE which also meets any of the serious criteria for SAEs.

Anticipated AEs associated with cataract surgery and/or premium IOL implantation that might reasonably be expected to occur in this study, however rare, are listed below and include, but are not limited to, the following:

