Anterior capsule tear

Anterior uveitis (including iritis and iridocyclitis) \*

Capsular block syndrome

Choroidal detachment/hemorrhage

Corneal edema \*

Cystoid macular edema (CME) \*

Difficulty with tasks in dim light resulting in secondary surgical intervention\*

Elevated IOP\*

Endophthalmitis (intraocular inflammation requiring vitreous tap and use of intraocular antibiotics)

Events resulting in unplanned secondary surgical intervention other than paracentesis to relieve pressure prior to 1 week postoperative or Nd:YAG capsulotomy

Flat anterior chamber

Hyphema

Hypopyon

Incorrect IOL power resulting in secondary surgical intervention \*

Increased glare or halos

Infectious keratitis

IOL damage resulting in secondary surgical intervention \*

IOL decentration or tilt \*

Iris or pupil damage

Loss of BCVA\*

Mechanical pupillary block (A shallowing of the peripheral and/or central anterior chamber with or without elevation of IOP by obstruction of the flow of aqueous humor from the posterior chamber through the pupil to the anterior chamber). This may be induced by the crystalline lens, vitreous face, or implanted devices.)

Multiple (or "ghost") images other than increased glare or halos

Pain \*

Posterior capsular rupture

Progression or onset of diabetic retinopathy

Progression or onset of macular degeneration

Reduced contrast sensitivity

Retained lens material

Retinal detachment (partial or complete RD associated with retinal tear)

Secondary IOL intervention (reposition, exchange, or removal) for any reason \*

Synechiae formation

Undesirable optical phenomena resulting in secondary surgical intervention

Thermal injury (phaco burn)

Toxic anterior segment syndrome (TASS) (An acute, noninfectious inflammation of the anterior segment of the eye that develops within 24 to 48 hours after surgery and is characterized by corneal edema and accumulation of white cells in the anterior chamber of the eye)

Vitreous prolapse

Wound leak (positive Seidel)

- \* These events may be considered normal or expected events after cataract surgery and only need to be reported as AEs/SAEs if present as specified below:
  - Iritis/cells/flare characterized by grade 1+ cells or greater using SUN criteria if persistent for greater than 3 months after surgery, or relapses in less than 3 months after discontinuation of therapy, or the subject is maintained on therapy for more than 3 months to control inflammation

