  - Corneal or corneal wound edema resulting in CDVA of ≤20/40 at Visit 3A or later in the first implanted eye or at Visit 3B or later in the second implanted eye, or any persistent corneal or corneal wound edema present at Visit 4
  - Cystoid macular edema diagnosed by clinical exam and adjunct testing (eg. OCT, FA or other method), resulting in CDVA of  $\leq$  20/40 at Visit 3 or later
  - Elevation of IOP by ≥10 mmHg above baseline (pre-operative) to a minimum of 25 mmHg after Visit 1A in the first implanted eye or after Visit 1B in the second implanted eye, or elevated IOP requiring treatment if present at Visit 4
  - Postoperative refractive error > 1.0 D different from predicted, and not due to calculation or other use error
  - Crack, breakage or deformity of IOL haptic or optic resulting in secondary surgical intervention

- IOL decentration or tilt likely to affect visual outcome and resulting in secondary intervention
- Monocular CDVA decrease of equal to or greater than 2 lines (≥10 letters) from any previous visit not secondary to any underlying condition, or any monocular CDVA decrease from any previous visit of greater than 2 lines if persistent to the subject's last visit in the study.
- Pain, per subjective patient reporting, graded as  $\geq 4$  on the standardized pain rating scale (from 0 to 10)
- Mild superficial punctate keratitis (SPK) present at Visit 3A or later in the first implanted eye or at Visit 3B or later in the second implanted eye, or moderate, severe, or very severe SPK at any post-operative visit (note: if SPK is present pre-operatively, adverse event must be reported only if there is a worsening)

Note: Posterior capsular opacification (PCO) is NOT to be reported as an AE unless the Investigator treats PCO with Nd:YAG laser exposure.

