# b. Relationship to Study Device or Surgical Procedure

- Related: There is at least a reasonable possibility the AE is related to the study device or surgical procedure. Reasonable possibility includes the following causality assessments:
  - O Possible: The relationship with the use of the investigational device or comparator, or the relationship with procedures, is weak but cannot be ruled out completely. Alternative causes are also possible (e.g. an underlying or concurrent illness/ clinical condition or/and an effect of another device, drug or treatment). Cases where relatedness cannot be assessed, or no information has been obtained should also be classified as possible.
  - o Probable: The relationship with the use of the investigational device or comparator, or the relationship with procedures, seems relevant and/or the event cannot be reasonably explained by another cause.
  - Causal relationship: the serious adverse event is associated with the investigational device, comparator or with procedures beyond reasonable doubt when:
    - the event is a known side effect of the product category the device belongs to or of similar devices and procedures;
    - the event has a temporal relationship with investigational device use/application or procedures;

- the event involves a body-site or organ that
  - the investigational device or procedures are applied to;
  - the investigational device or procedures have an effect on;
- the serious adverse event follows a known response pattern to the medical device (if the response pattern is previously known);
- the discontinuation of medical device application (or reduction of the level of activation/exposure) and reintroduction of its use (or increase of the level of activation/exposure), impact on the serious adverse event (when clinically feasible);
- other possible causes (e.g. an underlying or concurrent illness/ clinical condition or/and an effect of another device, drug or treatment) have been adequately ruled out;
- harm to the subject is due to error in use;
- the event depends on a false result given by the investigational device used for diagnosis, when applicable;

In order to establish the relatedness, not all the criteria listed above might be met at the same time.

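### Section 10.4.1 conflicts with itself on whether a refractive miss above 1.0 D attributed to calculation or use error must be reported; without secondary surgery, such a miss can go unrecorded as an adverse event

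*Combined protocol and SAP*

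**What the plan says.** Section 10.4.1 of the protocol sets the scope of collection: "For the purposes of this study, adverse events include: all ocular AEs". The same sentence adds serious adverse events, adverse device effects (ADEs) and serious ADEs. Of ADEs it says: "This definition also includes any event resulting from device malfunction, use error, inadequate labeling, or from intentional misuse of the investigational medical device". In Section 10.4.3, part b, one of the grounds for a causal relationship is that "harm to the subject is due to error in use".

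Section 10.4.1 then lists anticipated events. Those marked with an asterisk "only need to be reported as AEs/SAEs if present as specified below", and a set of threshold bullets follows. The bullet at issue is "Postoperative refractive error > 1.0 D different from predicted, and not due to calculation or other use error".

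Three entries in the anticipated-event list bear on it:

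- with an asterisk: "Incorrect IOL power resulting in secondary surgical intervention"
- without an asterisk: "Events resulting in unplanned secondary surgical intervention other than paracentesis to relieve pressure prior to 1 week postoperative or Nd:YAG capsulotomy"
- with an asterisk: "Secondary IOL intervention (reposition, exchange, or removal) for any reason"

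Section 10.4.4.4 separately treats use errors as device deficiencies to be reported to the sponsor. Under Section 7.2 the implanting investigator knows the lens assignment. Section 10.4.3 has the investigator judge seriousness, severity and relationship.

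**The concern.** Cause is normally assessed after an event has been recorded. Here it decides whether the event has to be recorded at all. Two eyes with the same miss from predicted refraction are treated differently according to the explanation the investigator gives, and that investigator may know which lens is in the eye. No other threshold bullet in Section 10.4.1 excludes use error.

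What is at stake is the completeness of the ocular adverse event and ADE record for a new lens model, and its consistency across up to about twelve sites. One site may follow the ADE definition and report; another may follow the threshold and not report. Nothing in the resulting counts would show which rule was used.

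**Working it through.** No figure in the plan needs recomputing, so the check sets the rules side by side.

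**Step 1: does the ADE definition reach these cases?** The bullet's own wording treats calculation error as one kind of use error, so both causes fall under the use-error term in the ADE definition. The bullet also accepts a miss above 1.0 D from any other cause as reportable. The size of the miss therefore already qualifies, and only the attributed cause takes it out.

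**Step 2: what force does the bullet have?** The lead-in relieves the site of the duty to report a starred event below its threshold. It does not forbid reporting. The result is that such an event can be missing, not that it must be.

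**Step 3: which cases are affected?** The bullet appears to belong to the starred incorrect-power entry. That pairing is inferred: bullets and asterisks do not match one to one. The bullet on superficial punctate keratitis has no starred entry, and the starred entry on difficulty in dim light has no bullet.

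| Case | ADE definition | Refractive threshold | Unstarred surgery entry | Result |
|---|---|---|---|---|
| Miss > 1.0 D, no surgery, other cause | depends on cause | met | not applicable | reportable |
| Miss > 1.0 D, no surgery, calculation or use error | included | not met | not applicable | **conflict; can go unrecorded** |
| Any miss leading to unplanned lens surgery, calculation or use error | included | not met | met | reportable, but may be lost under the incorrect-power term |

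The incorrect-power entry and the bullet also differ from each other. The entry requires secondary surgery and says nothing of size or cause; the bullet sets a size and a cause and does not mention surgery. The starred entry on lens intervention regardless of reason has no threshold at all, so its reporting condition is undefined.

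**Step 4: does another route catch the second row?**

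- The vision-loss threshold uses corrected distance acuity, so a refractive error alone need not trigger it.
- A device-deficiency report may exist, but it is not an adverse event record, and Section 11.4 describes no summary of deficiencies.
- Manifest refraction is measured through Visit 4, and the targeted refraction is recorded preoperatively (Appendix A). The miss can be derived from the data, but it is not thereby counted as an event.

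**Step 5: would the second row enter a primary safety count?**

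- Serious events: the criteria in Section 10.4.1 concern death, permanent impairment, hospitalization, threat to life or vision, intervention to prevent such harm, and fetal outcomes. A spectacle-correctable miss without surgery is not shown to meet any of them.
- Interventions due to the optics: Section 11.4.1.2 limits these to lens explantation, replacement or repositioning, so an eye without surgery is outside by definition.
- ISO grid events: the grid categories and rates are not in the documents, so membership cannot be shown.

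**Step 6: scale.** The synopsis gives about 224 Test eyes enrolled and about 200 expected to complete. One unrecorded Test eye changes a Test-group rate by 1/224 = 0.45 to 1/200 = 0.50 percentage points. The number of such eyes cannot be derived, because the documents give no rate of misses above 1.0 D and no split by cause.

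**The case against.** The strongest reply is that the rule loses little. The list of anticipated events is expressly open-ended. The entry on events leading to unplanned secondary surgery has no asterisk, no threshold and no use-error exception, so a wrong-power lens that has to be exchanged remains reportable whatever the cause. The use-error criterion in Section 10.4.3 applies to events already recorded and is not a reporting trigger. Use errors have a reporting channel in Section 10.4.4.4, and masked examiners measure refraction. The exclusion may also be a reasonable attempt to keep surgical planning errors from being charged to the lens.

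Most of this stands, and it confines the problem to misses without surgery. It does not remove the conflict there: the ADE definition includes the event and the threshold releases the site from reporting it. If the aim is to separate device performance from planning error, a recorded cause achieves that without losing the event.

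Three stronger readings are tempting but unsupported:

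- A reader might infer that wrong-power implants drop out of the primary safety counts. Surgical cases are kept by the unstarred entry, and non-surgical cases are not shown to belong to any of those counts.
- A reader might infer that Test events would be lost selectively, because a new model invites a calculation-error label. Nothing in the documents says so. A new model could equally invite attribution to the device, and both lenses come in the same power range and increments.
- A reader might infer an effect on the three primary acuity endpoints. Not reporting an adverse event does not by itself remove an eye's acuity measurements from analysis.

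**Conclusion.** The conflict is real and narrow. A miss above 1.0 D without secondary surgery, attributed to calculation or use error, is an ADE by definition but need not be reported under the threshold, so it can be absent from the ocular adverse event and ADE records. For surgical cases the defect is inconsistent classification, not demonstrated loss.

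The size is 0.45 to 0.50 percentage points of a Test-group rate per eye, with an unknown and probably small number of eyes. The conclusion rests on two readings of the text: that calculation error is a form of use error, as the bullet's wording implies, and that a miss above 1.0 D is untoward whatever its cause. The link between the bullet and the incorrect-power entry is inferred, and the main conflict does not depend on it. No change to a primary safety result and no imbalance between arms is established. The point is worth acting on because the correction is cheap and removes a filter that depends on unmasked attribution.

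**What to change.** Reconcile the ADE definition, the anticipated-event list and the threshold bullets in Section 10.4.1:

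1. Make the incorrect-power entry and its threshold describe the same event, with the role of secondary surgery stated in both or in neither, and say explicitly which bullet belongs to which starred entry.
2. Remove attributed cause as a condition of reporting. Record every event that meets the objective threshold as an adverse event.
3. Add one CRF field for attributed cause (calculation, other use error, device, other), so that use-error cases can be tabulated separately in each arm.
4. Give the starred lens-intervention entry a threshold, or remove its asterisk.

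The main change costs about one sentence in Section 10.4.1 and one CRF field; the targeted and measured refractions are already collected. The downside is a slightly higher reported count of ocular adverse events and ADEs, which the cause field would explain.

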#### 10.4.2 Identification and Collection

Identification and collection of an AE begins after informed consent has been obtained and documented. Standard sources of identifying AEs include:

- direct observation by the Investigator
- asking of the study participant a non-specific question (e.g., "Have you had any problems since the last visit?")
- unsolicited volunteering of information by the study participant (e.g., "Doctor, I have had blurred vision since I started using this lens.")
- laboratory or test results that meet protocol requirements for classification as an AE

Specific to this protocol, ocular AEs in the study eye(s) and all SAEs (ocular and non-ocular) observed or elicited by the Investigator, reported by the subject, or resulting from a test result, etc., occurring during the clinical investigation must be reported in the CRF for randomized subjects. For screen failures, AEs are recorded in the source data only, but not in the CRF. Note: The expedited reporting of SAEs with enrolled subjects as described below also applies for screen failures. During the study, the Investigator should treat the study subject as appropriate to ensure his/her safety and welfare. Refer to Section 10.4.5 for additional information pertaining to ongoing AEs at subject exit.

Pre-existing conditions will not be considered AEs but will be collected at the Preoperative Visit as medical history. A worsening of a pre-existing condition during the study should be documented as an AE and evaluated accordingly.

Hospitalizations for admission without a medical AE should be captured as a serious AE until the cause of hospitalization can be identified. However, the following reports of hospitalization without a medical AE should not be considered either serious or an AE:

- Admission for treatment of a pre-existing condition not associated with the development of a new AE or with worsening of the pre-existing condition (e.g., for work-up of persistent pretreatment lab abnormality)
- Social admission (e.g., subject has no place to sleep)
- Administrative admission (e.g., for yearly physical exam)
- Optional admission not associated with a precipitating medical AE (e.g., for elective cosmetic surgery)

#### 10.4.3 Evaluations

When evaluating AEs, the Investigator must determine if the event is serious or non-serious (refer to Section 10.4.1 for criteria), assess the severity of symptoms, and determine the relationship of the event to the device, using the following guidelines:

### a. Severity

- **Mild**: Subject awareness of a sign or symptom that is easily tolerated, requires no treatment, and does not interfere with subject's daily activities
- **Moderate**: Subject awareness of a sign or symptom which may be a low level of concern to the subject and may interfere with daily activities, but can be relieved by simple therapeutic care
- **Severe**: A sign or symptom that interrupts the subject's daily activity and requires systemic therapy or other treatment

# b. Relationship to Study Device or Surgical Procedure

- Related: There is at least a reasonable possibility the AE is related to the study device or surgical procedure. Reasonable possibility includes the following causality assessments:
  - O Possible: The relationship with the use of the investigational device or comparator, or the relationship with procedures, is weak but cannot be ruled out completely. Alternative causes are also possible (e.g. an underlying or concurrent illness/ clinical condition or/and an effect of another device, drug or treatment). Cases where relatedness cannot be assessed, or no information has been obtained should also be classified as possible.
  - o Probable: The relationship with the use of the investigational device or comparator, or the relationship with procedures, seems relevant and/or the event cannot be reasonably explained by another cause.
  - Causal relationship: the serious adverse event is associated with the investigational device, comparator or with procedures beyond reasonable doubt when:
    - the event is a known side effect of the product category the device belongs to or of similar devices and procedures;
    - the event has a temporal relationship with investigational device use/application or procedures;

- the event involves a body-site or organ that
  - the investigational device or procedures are applied to;
  - the investigational device or procedures have an effect on;
- the serious adverse event follows a known response pattern to the medical device (if the response pattern is previously known);
- the discontinuation of medical device application (or reduction of the level of activation/exposure) and reintroduction of its use (or increase of the level of activation/exposure), impact on the serious adverse event (when clinically feasible);
- other possible causes (e.g. an underlying or concurrent illness/ clinical condition or/and an effect of another device, drug or treatment) have been adequately ruled out;
- harm to the subject is due to error in use;
- the event depends on a false result given by the investigational device used for diagnosis, when applicable;

In order to establish the relatedness, not all the criteria listed above might be met at the same time.

- **Unrelated**: There is little or no reasonable possibility the AE is related to the study device or surgical procedure. No reasonable possibility means there is no evidence to suggest either a causal relationship or association between the study device or surgical procedure and the AE. No reasonable possibility includes the following assessments:
  - o the event has no temporal relationship with the use of the investigational device, or the procedures related to application of the investigational device;
  - o the serious adverse event does not follow a known response pattern to the medical device (if the response pattern is previously known) and is biologically implausible;
  - the discontinuation of medical device application or the reduction of the level of activation/exposure - when clinically feasible - and reintroduction of its use (or increase of the level of activation/exposure), do not impact on the serious adverse event:
  - o the event involves a body-site or an organ that cannot be affected by the device or procedure;
  - o the serious adverse event can be attributed to another cause (e.g. an underlying or concurrent illness/ clinical condition, an effect of another device, drug, treatment or other risk factors);
  - o the event does not depend on a false result given by the investigational device used for diagnosis, when applicable;

In order to establish the non-relatedness, not all the criteria listed above might be met at the same time.

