**Table 1. Non-serious Ocular Adverse Events** 

Non-serious ocular AEs	Non-device-related	Device-related
i Keduli ed Action	Recorded on Adverse Even no expedited report to Heal	t CRF only; th Canada, Sponsor, or IRB/IEC

Table 2. Serious Adverse Events

SAEs	Non-device-related	Device-related (SADE)
	-Recorded on SAE Report	-Recorded on SAE Report Form and
	Form and AE CRF.	AE CRF
Required Action	-Investigator submits expedited report to Sponsor and its representative within 48 hours.	-Investigator submits expedited report to Sponsor and its representative within 48 hours.
	-Report to IRB/IEC if required per IRB/IEC policy.	-Report to IRB/IEC within 10 days, or earlier if required per IRB/IEC policy.

	- Investigator must also submit SADE as a Mandatory Problem Report to HC within 72 hours of discovery.

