#### and

• Has led to the death or a serious deterioration in the state of health of a patient, user or other person, or could do so were it to recur. A serious deterioration in health means a life-threatening disease, disorder or abnormal physical state, the permanent impairment of a body function or permanent damage to a body structure, or a condition that necessitates an unexpected medical or surgical intervention to prevent such a disease, disorder or abnormal physical state or permanent impairment or damage. The term "permanent" means irreversible impairment or damage to a body structure or function, and necessarily excludes minor impairment or damage. Medical intervention is not in itself a serious deterioration in health. The reason that motivated the medical intervention should be used to assess the reportability of an incident.

For this protocol, all SADEs will be Mandatory Problems.

The contacts for Mandatory Problem Reporting for Health Canada are as follows:

Email: [contact]

Or

[contact]

Any reports which are reported to Health Canada as a Mandatory Problem, must also be submitted to the Sponsor per applicable timelines.

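### Adverse-event causality is rated on one scale that pools lens and surgery, while SADE status and expedited reporting depend on the device alone, and nothing links the two

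*Combined protocol and SAP*

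**What the plan says.** Section 10.4.3 (Evaluations) requires the investigator to "determine the relationship of the event to the device, using the following guidelines". The causality guideline that follows, item b, is headed "Relationship to Study Device or Surgical Procedure" and has two outcomes.

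- **Related:** "There is at least a reasonable possibility the AE is related to the study device or surgical procedure". It has three grades: Possible, Probable and Causal relationship. Each is worded to cover the device or the procedures. For Possible the text is "The relationship with the use of the investigational device or comparator, or the relationship with procedures, is weak but cannot be ruled out completely", followed by a default: "Cases where relatedness cannot be assessed, or no information has been obtained should also be classified as possible".
- **Unrelated:** this needs little or no reasonable possibility of a link to either the device or the operation.

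Section 10.4.1 defines the device categories differently. An ADE "is any adverse event related to the use of an investigational medical device or an approved medical device used as a comparator". A SADE is an ADE that also meets a seriousness criterion.

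In Section 10.4.4.1, Tables 1 and 2 split required actions by device-relatedness. The second column of Table 2 is headed "Device-related (SADE"). Section 10.4.4.2 ties ethics-committee reporting to device-related serious events. Section 10.4.4.3 adds: "For this protocol, all SADEs will be Mandatory Problems".

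**The concern.** The rating that investigators are told to make does not answer the question that the reporting rules ask. Every subject is scheduled for two cataract operations, so events arising from surgery are to be expected in both arms. Section 10.4.1 itself anticipates posterior capsular rupture, thermal injury, retained lens material and wound leak. On the supplied scale, such an event lands in the same class as an effect of the lens.

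What is at stake is the meaning of the SADE label. That label triggers a 72-hour report to Health Canada and is the trial's formal count of serious harm attributed to the device. If up to about twelve sites translate Related into device-related in their own ways, SADE and Mandatory Problem counts will not mean the same thing from site to site, and they may contain events in which the lens played no part.

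**Working it through.** No arithmetic applies. The plan states no figure on this point and gives no rate of surgical or lens complications. The check sets the relevant sections side by side.

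**1. The question and the tool.** The lead-in to Section 10.4.3 asks about the device. The scale beneath it asks about the device or the surgical procedure, in the heading, in Related and all its grades, and in Unrelated. It supplies no device-only rating.

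**2. What the later rules need.** The general adverse-event definition in Section 10.4.1 expressly takes in events linked to the procedures. The ADE definition in the same section does not. It mentions implantation only in connection with faulty instructions; its other extensions are malfunction, use error, inadequate labelling and intentional misuse. SADE status, the Table 2 columns and the rules in Sections 10.4.4.2 and 10.4.4.3 all build on that device-based definition.

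**3. Is there a bridge?** No section says that a pooled Related equals device-related, says how to split it, or asks for separate device and procedure ratings.

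**4. A test case.** Section 6.3.4 foresees a capsule tear or rupture during the first cataract extraction, and also foresees randomized subjects in whom no lens was inserted. Suppose a capsule ruptures before lens insertion and the event meets a seriousness criterion.

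- On the 10.4.3 scale it is Related, because the procedure caused it.
- By the 10.4.1 definition it is not an ADE, because no study lens had been used in that eye. It is therefore not a SADE.
- Table 2 must place it in one of two columns, with different duties:

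| Duty in Table 2 | Non-device-related | Device-related |
|---|---|---|
| Sponsor and its representative | 48 hours | 48 hours |
| Ethics committee | only if its policy requires | 10 days, or sooner if its policy requires |
| Health Canada | none listed | 72 hours |

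(Section 10.4.4.2 says 10 working days for the ethics committee; that difference is a separate matter.)

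A site that follows the scale chooses the right-hand column. A site that follows the definition chooses the left-hand one. Both can point to protocol text.

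**5. Does a later test catch it?** Section 10.4.4.3 first limits Mandatory Problems to incidents involving device failure, loss of effectiveness, or inadequate labelling or directions, with serious actual or potential harm. The blanket statement about SADEs then makes the label sufficient by itself, so that screen would not remove a misplaced surgical event.

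**6. The default.** An event that cannot be assessed becomes Possible, and so Related. On a pooled scale it cannot be said whether the doubt concerns the lens, the operation or both.

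**7. Where the rating is not used.** Section 11.4.1.1 counts eyes with any serious event, whatever the cause. Section 11.4.1.3 counts ISO grid events, whatever the cause. Section 11.4.1.2 gives secondary surgical interventions their own attribution to the optical properties of the lens. Sections 11.4.2.1 and 11.4.2.2 summarize visual disturbance and contrast sensitivity directly by treatment. Table 1 has one shared action for both columns, so misclassification there changes a label and nothing else.

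**The case against.** The best reply is that the protocol permits the correct answer. The lead-in to 10.4.3 says device, the ADE definition says device, and Table 2 keeps a non-device-related column. Section 10.4.4.2 also provides for serious events that are not device-related. An investigator who reads all of these together will put a purely surgical event in the non-device column. This stands as far as it goes: a reader might infer that every serious surgical complication must be reported as a SADE, and the documents do not say that. But reaching the correct answer means setting aside the only scale provided, and nothing tells the investigator to do so.

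A second reply is that any error is cautious. All serious events reach the sponsor within 48 hours in either column, and both the blanket SADE rule and the default to Possible favour reporting. This also stands, and no loss of a safety signal is claimed here. What remains is inconsistency, and counts that may include events of surgical origin only.

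Third, the case report form is not among the documents and may already hold two fields. The wording could also be applied to device and procedure in turn. That cannot be excluded, but the protocol text requires only one rating. If two fields exist, aligning the text costs almost nothing.

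Finally, a reader might infer that pooling hides a difference between the trifocal and monofocal lenses in the safety results. The documents do not support this. No planned analysis uses the rating, no table of related events or SADEs by arm is specified, and the randomized control group undergoes the same surgery.

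**Conclusion.** The inconsistency is real and goes beyond missing detail: applied as written, the scale cannot yield the device-only classification on which SADE status, the device-related column of Table 2, ethics-committee reporting and Mandatory Problem reporting depend. A serious event due to surgery alone is Related on the scale and not an ADE by definition, and sites may resolve this in different ways.

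The reach is limited to ADE and SADE classification, expedited reporting, and any count built on those labels. The primary safety endpoints and the Table 1 actions are unaffected. How many events would be misplaced cannot be estimated from the documents. The conclusion assumes that the protocol text governs and that no form or manual outside these documents already separates the two ratings.

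**What to change.** Reconcile Section 10.4.3 with Section 10.4.1, Tables 1 and 2, and Sections 10.4.4.2 and 10.4.4.3:

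- Record causality twice for each event on the existing scale: once for the study lens, including its injector and its use, and once for the surgical procedure. Allow both to be marked.
- State that ADE and SADE status, and the device-related columns of both tables, follow from the lens rating alone.
- Apply the default for unassessable cases to each rating separately, so that an uncertain lens contribution stays reportable.
- Tabulate the two ratings separately by arm.

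The cost is one extra case report form item per event, a short text change and a small additional table. The drawback is that investigators must use some judgement to separate the two causes; allowing both to be marked eases this.
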